11. SAFETY ANALYSES

All safety summaries will be based on the safety population. No formal statistical testing will be performed to compare the safety in different treatments. Unscheduled and PEx visits will not be included in safety by visit tables, but will be included in a listing, by subject.

11.1. Adverse Events

Throughout the duration of the study, the investigator or designees will closely monitor each subject. All AEs which occur during the study, whether observed by the investigator or by the subject, and whether or not thought to be related to study drug will be recorded. The description of the AEs as recorded on the eCRF will include a description of event, start date, stopping date, intensity, if it was serious, relationship to study drug, what actions were taken with respect to the study drug, if treatment was required and the subject's outcome.

The investigator must evaluate each AE for its relationship to the study drug and for its seriousness. All AEs related to study drug must be followed until resolution or until they become stable.

AEs will be coded using Medical Dictionary for Regulatory Activities, Version 22.1.

Treatment-emergent AEs include all AEs onset between first dose and last dose of the study product, inclusive. TEAEs and AE onset during the 28-day follow-up will be summarized separately. Any AEs that occur before first dosing will be summarized in a table as Pre-Treatment AEs.

An overall summary by treatment cohort will be presented that includes the number and percentage of subjects who experienced at least one TEAE, serious TEAE, TEAEs by maximum severity, TEAEs by strongest relationship to study product, TEAEs leading to study product withdrawal, TEAE of dizziness ([Section 11.2](#)), and death. The total number of TEAEs will also be presented. The overall summary of TEAEs will also be presented by age group (< 18 years and \geq 18 years).

The number and percentages of subjects with the TEAEs listed below will be summarized by SOC, preferred term, and treatment separately. The TEAEs listed below will also be summarized by age group (< 18 years and \geq 18 years). If a subject reports the same preferred term multiple times within the same SOC, that subject will only be counted once for the SOC. As with the preferred term, if a subject reports multiple conditions within the same preferred term, that subject will only be counted once for the preferred term.

- TEAEs
- Serious TEAEs
- TEAEs leading to study product withdrawal
- TEAEs of dizziness (AE of special interest)
- TEAEs by maximum severity
- TEAEs by strongest relationship to study product
- TEAEs in \geq 2% of subjects in lenabasum 20 mg BID cohort
- TEAEs of abuse potential; relevant preferred terms include the following:

Anxiety, apathy, bradykinesia, bradyphrenia, cognitive disorder, confusional state, depressed level of consciousness, depressed mood, depression, derealization, disorientation, dissociation, disturbance in attention, dizziness, dyskinesia, dysphoria, elevated mood, euphoric mood, feeling abnormal, feeling drunk, feeling jittery, feeling of relaxation, hallucination, hyperflexia, hypersomnia, hypoesthesia, hypoflexia, inappropriate affect, insomnia, lethargy, malaise, mental disorder, mental impairment, mobility decreased, mood altered, nervous system disorder,

nervousness, neuralgia, panic attack, paraesthesia, restlessness, sleep disorder, sluggishness, somnolence, stupor, thinking abnormal, vision blurred, visual disturbance, visual impairment, sensory disturbance, amnesia, irritability, memory impairment, agitation, and any other related terms

The total number of TEAEs by SOC and preferred term will also be presented.

Similar to TEAEs tables, another set of tables for follow-up AEs will be provided.

In addition to an overall AE listing, serious AEs, AEs leading to study product withdrawal, fatal AEs, and AEs of special interest will also be presented in subject data listings.

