Suspected Unexpected Serious Adverse Reaction:	An adverse event that (a) meets the definition of a serious adverse event, (b) the nature or severity of which is not consistent with study product information in the Investigator's Brochure, and (c) there is reason to suspect that the study product caused the event.
Tolerability:	The incidence of discontinuation of study product or "drop-out" due to a treatment emergent adverse event probably or definitely related to study product.
Treatment:	Term used throughout the protocol to denote the study product or placebo intended to be administered to a subject.
Treatment-emergent adverse event:	Any event not present before the initiation of the treatments or any event already present that worsens in either intensity or frequency following exposure to the treatments.

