4. STUDY DESIGN AND PLAN AND STUDY ENDPOINTS

4.1. Study Design and Plan

This is a randomized, double-blind, placebo-controlled, multicenter, interventional, parallel-dose Phase 2b study to assess the efficacy and safety of treatment of CF subjects with lenabasum 20 mg BID and lenabasum 5 mg BID. Subjects will be randomized 2:1:2 to receive blinded study product (lenabasum 20 mg BID, lenabasum 5 mg BID, or placebo BID) for 28 weeks.

[figure not shown]
Active dosing with study product is 28 weeks. There will be 8 scheduled study visits during active dosing with study product, labeled Visits 1-8, which occur at Visit 1 and at the completion of Weeks 4, 8, 12, 16, 20, 24, and 28.

Subjects who complete Visit 8 on study product will have a Safety Follow-up Visit, labeled Visit 9, at 28 ± 7 days after Visit 8, at all study locations except for those in France.

[figure not shown]
All subjects who develop acute signs and symptoms of possible worsening respiratory disease will be asked to return to the site, as possible, for evaluation at a Possible PEx Visit.

Unscheduled Visits may be necessary to assess the subject for safety purposes unrelated to new respiratory symptoms or a PEx. If a new PEx and associated tests are recorded at an Unscheduled Visit rather than a Possible PEx Visit, that PEx information and any associated efficacy or biomarker assessments done at the Unscheduled Visit will be handled as if the Unscheduled Visit were a Possible PEx Visit.

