4.1.12. Discontinuation from Study Product but Continuation in Study

A subject may discontinue study product and continue in the study. If a subject permanently discontinues study product, they will be asked to continue in the study for efficacy and safety follow-up with Visits 5 and 8 performed off study product, starting with the next one of these visits that occurs after discontinuation of study product. For subjects who do not withdraw consent and agree to return for these visits, an additional 28-day safety follow-up after Visit 8 will not be done. Safety and efficacy data will be collected during these visits and included in analyses of safety and efficacy data. The impact of having these subjects remain in the study will be assessed in sensitivity analyses of the primary and first secondary efficacy outcomes.

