9.2. Discontinuations, Lost to Follow-up, and Unscheduled Visits

All assessments of efficacy and safety done after discontinuation of study drug will be included in primary efficacy and safety analyses, for subjects who permanently discontinue study product, do not withdraw consent, and continue in the study.

If a subject withdraws consent, their last regularly scheduled study visit before withdrawing consent will be their last visit for efficacy and safety assessments.

If a subject is lost to follow-up, their last regularly scheduled study visit that they attended will be considered their last visit.

Efficacy assessments done at Unscheduled Visits and Possible PEx visits will be counted in efficacy analyses, only if AUQ-R at that visit indicates that the subject is having a PEx that meets primary or secondary definitions of a new PEx. Otherwise, efficacy assessments done at unscheduled visits and Possible PEx visits will be included only in listings.

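### AEs that start after the last dose in subjects who stop product but stay in the study enter none of the general AE summary tables, although Sections 4.1.12 and 9.2 include these data

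*SAP*

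**What the plan says.** Section 11.1 sets the treatment-emergent window: "Treatment-emergent AEs include all AEs onset between first dose and last dose of the study product, inclusive". Two other windows have tables. One is pre-treatment: "Any AEs that occur before first dosing will be summarized in a table as Pre-Treatment AEs". The other is follow-up: "TEAEs and AE onset during the 28-day follow-up will be summarized separately", with the later statement "Similar to TEAEs tables, another set of tables for follow-up AEs will be provided".

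Section 4.1 gives the follow-up visit to a defined group: "Subjects who complete Visit 8 on study product will have a Safety Follow-up Visit". Section 4.1.12 covers subjects who permanently stop product and continue in the study. They are seen at whichever of Visits 5 and 8 still lie ahead, and for them "an additional 28-day safety follow-up after Visit 8 will not be done". The same section says that the data from those visits enter the safety and efficacy analyses.

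Section 9.2 repeats that commitment for the same subjects: "All assessments of efficacy and safety done after discontinuation of study drug will be included in primary efficacy and safety analyses". The glossary (Section 1.2) defines a TEAE as "Any event not present before the initiation of the treatments or any event already present that worsens in either intensity or frequency" after exposure, with no closing date. Section 13 bases the safety analyses generally on a treatment period that runs to Week 28, or to discontinuation for those who leave the study early, with follow-up AEs summarised separately.

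**The concern.** TEAEs by cohort are the primary safety endpoint (Sections 3.4 and 4.3.1). The SAP keeps subjects under observation after they stop product and promises to analyse what is seen, but the section that defines the AE tables has no place for events that start in that period. A serious AE starting the day after the last dose in such a subject would not be a serious TEAE, nor would it belong to the 28-day follow-up. It would be found only in listings, which give no comparison between cohorts. AEs that arise on stopping product early are among those lost.

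The SAP also gives more than one rule for what is treatment-emergent. Two programmers, one working from the glossary and one from Section 11.1, could produce different primary safety tables from the same data.

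**Working it through.** The SAP gives no figure to reproduce. The check maps AE onset dates to tables and then compares the rules.

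**Step 1: where an AE goes.** Take a subject who permanently stops product on Day *s* and stays to Visit 8, assumed to fall on Day 196 (28 × 7).

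| Onset | Table under Section 11.1 |
|---|---|
| Before first dose | Pre-treatment |
| Day 1 to Day *s* | TEAE |
| Day *s* + 1 to Day 196 | None: not pre-treatment, after the last dose, and no 28-day follow-up for this subject |

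**Step 2: length of the gap.** Uncovered days = 196 − *s*. For an assumed *s* = 60, this is 196 − 60 = 136 days. If the 28-day follow-up is read as the 28 days after the last dose, uncovered days = 196 − *s* − 28, which is 108 for the same subject. On that reading the gap closes only if *s* is Day 168 or later (196 − 28 = 168). Depending on the day of stopping, the gap in Section 11.1 as written runs from near 0 to near 28 weeks.

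**Step 3: the rules side by side.** For a new AE on Day 61 in the same subject:

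- Section 11.1: not a TEAE and in no other general table.
- Glossary: a TEAE, because it was not present before treatment began.
- Sections 4.1.12 and 9.2: part of the safety analyses.
- Section 13: inside the treatment period, because the subject has not left the study and Week 28 has not been reached.

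For a pre-existing AE that worsens on product, the glossary counts a TEAE. Section 11.1 looks only at onset and does not say that a worsening receives its own onset date.

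**Step 4: other places the events could appear.** The dizziness table in Section 11.2 is cumulative to Visit 8 and could hold dizziness events from the gap, although its occurrence-period rows cover only time on active drug and the safety follow-up. The death row of the overall summary in Section 11.1 and the COVID-19 event table in Section 4.1.14 are not expressly limited to TEAEs. The overall, serious and fatal AE listings would show the events subject by subject. None of these is a general summary of AEs by cohort.

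**Step 5: rough scale, on assumptions only.** Planned follow-up is 415 × 28 = 11,620 subject-weeks. Suppose 5% to 10% of subjects stop and stay (about 21 to 42), on average halfway, leaving 14 weeks each.

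- As Section 11.1 is written: 21 × 14 = 294 to 42 × 14 = 588 subject-weeks, or 2.5% to 5.1%.
- With the 28 days after the last dose covered, 10 weeks remain: 21 × 10 = 210 to 42 × 10 = 420 subject-weeks, or 1.8% to 3.6%.

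These are shares of observation time, not of events. Neither the 5% to 10% nor the halfway stop comes from the SAP. The drop-out of about 15% in Section 4.1.5 is a different quantity.

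**The case against.** The best defence is that the text can be read to fill the gap. Section 4.1.12 calls the off-product visits safety follow-up and withholds only an additional 28 days. The introduction describes the 28-day follow-up as a period off study product. The sentence promising follow-up AE tables does not repeat the 28-day limit. A programmer might therefore place some or all of these events in the follow-up tables. This shows that the intent may have been inclusive, but Section 11.1 ties the separate summary to the 28-day follow-up. Counting 28 days from the last dose shortens the gap without closing it, and sits badly with Section 4.1.12.

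A second defence is that an on-treatment TEAE window is a legitimate choice. It is, provided that it is used consistently and that off-treatment AEs have a table. Neither holds here.

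A reader might infer more than the SAP supports:

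- That all AEs of early stoppers are lost. They are not: those starting on or before the last dose are TEAEs. An AE that causes stopping normally starts by then, so it is also counted among TEAEs leading to withdrawal.
- That the omitted events appear nowhere. The listings show them, and the dizziness table, death row and COVID-19 table may.
- That the loss falls mainly on one arm. The SAP gives no discontinuation data by arm.

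**Conclusion.** The contradiction stands. Followed as written, Section 11.1 leaves AEs with onset after the last dose and up to Visit 8, in subjects who stay in the study off product, out of every general AE summary table. Sections 4.1.12 and 9.2 say those data are analysed. The glossary and Section 13 each set a different window, and the glossary also counts worsening.

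The effect is limited to this group and this period, and to loss from the cohort summaries rather than from the record. The length of the gap depends on the day of stopping. The number of subjects and any imbalance between arms are not stated, so the shares of observation time worked out above are illustrations only. The primary efficacy result is not affected. The point deserves correction because it concerns the primary safety endpoint and needs no new data.

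**What to change.** Use one TEAE definition, including worsening of pre-existing events, in Sections 1.2, 9.2, 11.1, 11.2 and 13. State which table holds each AE with onset after the last dose, up to Visit 8 or study exit, and summarise those AEs by cohort.

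The simplest way keeps the on-product TEAE tables and widens the existing follow-up AE tables to all AEs starting after the last dose. Off-product subjects should be shown separately from the completers' 28-day follow-up. Extending the TEAE window to 28 days after the last dose for everyone is not needed: it would move completers' follow-up AEs into the main tables, and the SAP deliberately keeps them apart.

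The cost is SAP wording and one more derivation flag, with no new data collection. The drawback is that some tabulated AEs will be remote from dosing, which the separate display makes visible.

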4.3. Study Safety Endpoints

4.3.1. Primary Safety Endpoints

- TEAEs by treatment cohorts and combined lenabasum cohorts

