8.2. Study Treatments

8.2.1. Extent of Exposure

Treatment exposure duration will be defined as the number of days that the subject was exposed to study treatment as calculated using the formula:

$$\text{Exposure duration (days)} = \text{date of last dose} - \text{date of first dose} + 1.$$

Last dose date will be imputed using last contact date during active treatment for the subjects lost to follow up and as the date of the last visit seen, excluding safety follow-up visit, for subjects missing last dose date.

The duration of exposure will be summarized for treatment cohorts and combined lenabasum cohort. All summaries will be based on the safety population. Summary statistics will be presented for treatment exposure.

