9.1. Handling of Missing Data

Missing data will not be imputed for efficacy and safety analyses unless specified otherwise. See [Section 4.1.14](#) for handling data during COVID-19 pandemic.

If start or end date of antibiotics is incomplete:

- Missing start day only: If month and year are the same as first dose date of study product, impute the antibiotics start date using first dose date of study product, impute the missing day using '01'
- Missing start day and month, but year not missing: If year is the same as first dose date of study product, impute the antibiotics start date using first dose date of study product. If year is not the same as first dose date, impute the missing day using '01' and the missing month using 'Jan'
- Start date missing completely: impute the missing date using first dose date of study product
- Missing end day only: impute the missing end day using the last day of the month
- Missing end day and month, but year not missing: impute the missing day using '31' and missing month using 'Dec'
- Missing end date completely: impute using last visit date

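### SAP section 11.1 assigns AEs by onset date alone, which contradicts the glossary's rule that a pre-existing event worsening on treatment is a TEAE

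*SAP*

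**What the plan says.** The primary safety endpoint in SAP section 4.3.1 is "TEAEs by treatment cohorts and combined lenabasum cohorts". The SAP defines a TEAE in two places.

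- **Section 1.2, Glossary.** A TEAE is an event that was absent before treatment began, or "any event already present that worsens in either intensity or frequency following exposure to the treatments".
- **Section 11.1, Adverse Events.** "Treatment-emergent AEs include all AEs onset between first dose and last dose of the study product, inclusive". It continues: "Any AEs that occur before first dosing will be summarized in a table as Pre-Treatment AEs". AEs that begin in the 28-day follow-up are summarized separately. Section 11.1 neither mentions worsening nor refers back to the glossary.

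On incomplete data, section 9.1 says: "Missing data will not be imputed for efficacy and safety analyses unless specified otherwise". The date rules that follow it open with "If start or end date of antibiotics is incomplete" and cover antibiotics only. Section 8.2.1 adds one more date rule: "Last dose date will be imputed using last contact date during active treatment for the subjects lost to follow up". The text at hand has no rule for an incomplete AE onset date.

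**The concern.** Section 11.1 is the section a programmer would normally follow, and it gives the lower count. Screening can run for up to 28 days (section 4.1.6), so complaints can be on record before the first dose. Section 11.2 asks for past history of dizziness, which suggests that its authors expected some subjects to arrive with the complaint of special interest. Several of the abuse-potential terms in 11.1, such as insomnia, anxiety and irritability, can also be present at entry and become worse.

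An onset-only rule removes from the primary safety tables the part of the drug's effect that shows as aggravation of an existing complaint. The rule is the same in every cohort. If the product does aggravate such complaints, however, more events would be lost from the active cohorts than from placebo. Nothing in the SAP shows that it does.

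Onset date alone decides the table in which an AE appears, yet the SAP sets rules for incomplete antibiotic dates and missing last-dose dates and none for this date.

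**Working it through.** The SAP states no figure on this point, so the check is to apply both definitions to the same AEs.

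| AE | Glossary, 1.2 | Section 11.1 |
|---|---|---|
| Begins on product, up to last dose | TEAE | TEAE |
| Begins in screening, does not worsen | Not a TEAE | Pre-Treatment |
| Begins in screening, worsens on product, kept as one record | TEAE | Pre-Treatment |
| Begins in screening, worsening entered as a new AE dated on product | TEAE | New record is a TEAE |

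The two sections disagree in the third row only. Whether a given event falls in the third or the fourth row depends on how sites record worsening. The SAP does not say. The eCRF items listed in 11.1 include a start date, a stop date and intensity, but no date of worsening.

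**Effect of one reclassified subject.** With the planned cohort sizes in section 4.1.9, one subject moves the percentage for a term by 1/166 = 0.6 points in the 20 mg or placebo cohort and by 1/83 = 1.2 points in the 5 mg cohort. The table of TEAEs in at least 2% of the 20 mg cohort needs 4 subjects (3/166 = 1.8%; 4/166 = 2.4%). At exactly 4, losing one subject's only record of the term removes the term from that table, though not from the full table by preferred term. These figures show what one subject is worth. They do not estimate how many subjects are affected.

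**Incomplete onset dates.**
- A wholly missing onset date cannot be placed by 11.1 unless other information, such as a stop date before first dose, settles it.
- A date known to month and year can be placed whenever that month lies wholly inside or outside the dosing window. Full dosing is 28 x 7 = 196 days. The longest run of six calendar months is 184 days, so 196 days touch at least 7 calendar months. At most 2 of these contain the first or last dose, so at least 7 - 2 = 5 lie wholly inside the window for a subject who completes dosing.
- The gap is therefore confined to wholly missing dates and to partial dates that straddle first or last dose.

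**The case against.** The strongest reply is that nothing has been excluded. The glossary expressly counts worsened events, and the verb in 11.1 says what TEAEs include without saying that they include nothing else. If sites enter a worsening as a new AE, the event falls inside the 11.1 window. The protocol and CRF instructions that might require this are not at hand. This much stands: a reader might infer that worsened events can never reach the TEAE tables, and the SAP does not support that. But 11.1 also sends AEs occurring before first dosing to another table without exception, and the SAP does not say that worsening is recorded as a new AE. The contradiction remains.

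A reader might also infer that section 9.1 forbids any imputation of AE dates, so that every incompletely dated AE is dropped. That goes too far. Section 9.1 allows exceptions, 8.2.1 makes one for the last dose date, and most partial dates need no imputation. For the rest the SAP is silent; it does not say that they are dropped.

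Nor does the SAP lose TEAEs with missing severity or relationship. Section 6.1 provides a Missing row in count tables, and such events still count in the tables by preferred term.

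The practical loss is also limited. For AEs of dizziness, 11.2 plans a summary through Visit 8 with maximum severity, and narratives from Grade 2 upward. Section 11.1 keeps every event visible: "In addition to an overall AE listing, serious AEs, AEs leading to study product withdrawal, fatal AEs", and AEs of special interest, are listed. Section 11 plans no formal safety testing. These safeguards reduce the harm, but a listing does not correct the percentages in the primary safety tables.

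**Conclusion.** Sections 1.2 and 11.1 contradict each other on AEs that begin before first dose and worsen on product, and they need to be reconciled. Followed literally, 11.1 undercounts the primary safety endpoint against the SAP's own definition. This conclusion assumes that 11.1 is programmed as written and that the worsening is not entered as a separate AE. Where it is entered separately, nothing is lost. The size cannot be estimated, because the SAP gives neither the frequency of worsened screening AEs nor the recording rule. No efficacy result is affected.

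The missing rule for onset dates is a smaller omission, limited to wholly missing dates and to partial dates that straddle a dosing boundary.

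**What to change.** In section 11.1, replace the start of the TEAE definition with the one in the glossary: onset on or after first dose, or present before first dose and worsening in intensity or frequency after it. State that the worsened event is tabulated as a TEAE at its worst on-treatment grade, and say how worsening is identified from the eCRF. Limit the Pre-Treatment table to AEs that begin before first dose and do not worsen afterwards. This change concerns the start of the window only and leaves its end as it is.

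As a minor addition, in 9.1 or 11.1, state that an AE whose onset date is wholly missing, or whose partial date straddles first or last dose, is treated as treatment-emergent unless the known date parts rule it out. Show the date as recorded in the listing.

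The cost is a few sentences and a change to the derivation code. TEAE counts may rise slightly. Section 2 allows no sponsor change after signature other than analyses requested by FDA, so the correction belongs before signature. If the SAP is already signed, the definition actually applied should be reported in the CSR, as section 14 provides.
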